**8.5 Subsequent Assessments**

Each participant will have blood taken via a normal hypodermic needle and a new non luer one-way valve filter needle. The blood taken with each needle will undergo near patient TEG testing. This will represent the end of the participants research participation

8.6 Definition of End of Trial

The end of trial will be the completion of the 30th paired TEG test in the pregnant group and the 10th in the volunteer group.

8.7 Discontinuation/Withdrawal of Participants from Study Treatment

Each participant has the right to withdraw from the study at any time. In addition, the investigator may discontinue a participant from the study at any time if the investigator considers it necessary for any reason including:

Ineligibility (either arising during the study or retrospective having been overlooked at screening)

Significant protocol deviation

Significant non-compliance with treatment regimen or study requirements

An adverse event which requires discontinuation of the study or results in inability to continue to comply with study procedures

Developing a medical condition

Consent withdrawn

Lost to follow up

If participants are withdrawn from the study they will be replaced and data acquired from withdrawn participants will be destroyed. The reason for withdrawal will be recorded in the CRF.

If the participant is withdrawn due to an adverse event, the investigator will arrange for follow-up visits or telephone calls until the adverse event has resolved or stabilised.

8.8 Source Data

Source documents are original documents, data, and records from which participants' CRF data are obtained. These include, but are not limited to, hospital records (from which medical history and previous and concurrent medication may be summarised into the CRF), clinical and office charts, laboratory and pharmacy records, diaries, radiographs, and correspondence.

CRF entries will be considered source data if the CRF is the site of the original recording (e.g., there is no other written or electronic record of data). In this study the CRF will be used as the source document to aid recruitment of participants from the preassessment elective caesarean section clinic.

All documents will be stored safely in confidential conditions. On all study-specific documents, other than the signed consent, the participant will be referred to by the study participant number/code, not by name.

9. TREATMENT OF TRIAL PARTICIPANTS

9.1 Description of Study Treatment

Participant involvement in the study involves allowing phlebotomy to be taken with the two different needles.

9.2 Storage of Study Equipment or Related apparatus

The new non-Luer one-way valve filter needles will be stored in the anesthetic office situated in the maternity unit at Leicester Royal Infirmary.

10. SAFETY REPORTING

10.1 Definitions

10.1.1 Adverse Event (AE)

An AE or adverse experience is:

Any untoward medical occurrence in a patient or clinical investigation participants, which does not necessarily have to have a causal relationship with this treatment.

An AE can therefore be any unfavourable and unintended sign (including an abnormal laboratory finding), symptom or disease temporally associated with the the study, whether or not considered related to the study.

10.1.2 Adverse Reaction (AR)

All untoward and unintended responses related to the study.

All cases judged by either the reporting medically qualified professional or the sponsor as having a reasonable suspected causal relationship to the study qualify as adverse reactions.

10.1.3 Severe Adverse Events

To ensure no confusion or misunderstanding of the difference between the terms "serious" and "severe", which are not synonymous, the following note of clarification is provided:

The term "severe" is often used to describe the intensity (severity) of a specific event (as in mild, moderate, or severe myocardial infarction); the event itself, however, may be of relatively minor medical significance (such as severe headache). This is not the same as "serious," which is based on patient/event outcome or action criteria usually associated with events that pose a threat to a participant's life or functioning. Seriousness (not severity) serves as a guide for defining regulatory reporting obligations.

10.1.4 Serious Adverse Event or Serious Adverse Reaction

A serious adverse event or reaction is any untoward medical occurrence that at any dose:

- Results in death,
- Is life-threatening,

NOTE: The term "life-threatening" in the definition of "serious" refers to an event in which the participant was at risk of death at the time of the event; it does not refer to an event which hypothetically might have caused death if it were more severe.

- Requires inpatient hospitalisation or prolongation of existing hospitalisation,
- Results in persistent or significant disability/incapacity, or
- Is a congenital anomaly/birth defect.
- Other important medical events*

*Other events that may not result in death, are not life threatening, or do not require hospitalisation, may be considered a serious adverse event when, based upon appropriate medical judgement, the event may jeopardise the patient and may require medical or surgical intervention to prevent one of the outcomes listed above.

10.1.5 Expected Serious Adverse Events/Reactions

This study is not expected to cause any serious adverse events or reactions. The main issues to note would be difficult phlebotomy which would be uncomfortable and phlebotomy can lead to bruising. None of these would require reporting.

10.1.6 Suspected Unexpected Serious Adverse Reactions

A serious adverse reaction, the nature or severity of which is not consistent with the applicable product information

10.2 Reporting Procedures for All Adverse Events

All AEs occurring during the study observed by the investigator or reported by the participant, whether or not attributed to study, will be recorded on the CRF.

The following information will be recorded: description, date of onset and end date, severity, assessment of relatedness to study, other suspect device and action taken. Follow-up information should be provided as necessary.

AEs considered related to the study as judged by a medically qualified investigator or the sponsor will be followed until resolution or the event is considered stable. All related AEs that result in a participant's withdrawal from the study or are present at the end of the study, should be followed up until a satisfactory resolution occurs.

Any abnormal results from the laboratory full blood count or clotting profile will be shared with the patient, the patients clinical team or GP in the case of the volunteer limb.

It will be left to the investigator's clinical judgment whether or not an AE is of sufficient severity to require the participant's removal from treatment (see section 7.7). A participant may also voluntarily withdraw from treatment due to what he or she perceives as an intolerable AE. If either of these occurs, the participant must undergo an end of study assessment and be given appropriate care under medical supervision until symptoms cease or the condition becomes stable.

The severity of events will be assessed on the following scale: 1 = mild, 2 = moderate, 3 = severe.

The relationship of AEs to the study will be assessed by a medically qualified investigator.

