4. BACKGROUND AND RATIONALE

Patient safety agencies such as the National Patient Safety Agency (NPSA) and European Medicines Agency recommend adoption of equipment that prevents wrong route drug administration¹. For example medicine intended for the intravenous route should not be possible to be given via the epidural route, hence limiting potentially catastrophic complications associated with human error². However, the epidural blood patch requires equipment that connects to the intravenous and epidural route, as blood is taken from a patient's vein and then it is injected into the patient's epidural space for therapeutic effect. Hence equipment is required that allows blood aspiration from the patient but does not have the potential to inject into the patient hence complying with patient safety agency recommendations. Aspirating blood from the patient via a non-Luer one-way filter valve has the theoretical potential of activating the clotting cascade. If this occurred it could reduce the time the clinician has to utilise the blood before it clots in the syringe. Changes in clotting characteristics also has unknown implications when injected into the epidural space with regards to the therapeutic effect of the procedure.

The epidural blood patch is mainly used in obstetric anaesthesia in the treatment of dural puncture headaches, however it is also used to treat conditions such as spontaneous intracranial hypotension, hence this study involves post natal and non-pregnant populations. This study requires blood to be taken from the study participants via a venepuncture. This will require 12mls of blood to be taken from the patient via a standard 21G hypodermic needle and also 2mls of blood via the new 21G non-Luer one-way filter valve needle. The blood will undergo clotting profile testing. The implications for study subjects would be two venepunctures and a total of 14mls of blood taken. The post natal population would only require one additional venepuncture with the new one-way valve needle as they would already be having bloods taken for their day 2 post elective cesarean section bloods, an additional 9ml of blood only.

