6. STUDY DESIGN

6.1 Summary of Trial Design

This study will be an observational study. The pregnant participants will be recruited from the elective pre-operative caesarean clinic and have their bloods taken on day 2 post natal after their elective caesarean section during their routine full blood count testing.

The healthy non-pregnant participants will be recruited via posters in the University Hospitals of Leicester.

The blood taken via the two different needles will be analysed via near patient testing with Thromboelastography (TEG) analysis and this will be the end of their study participation.

We will alternate between patients with regards to which needle will be used first during phlebotomy (ie hypodermic needle vs new non-Luer one-way valve filter needle). The punctures will be from separate veins for each of the two needles.

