10.3 Reporting Procedures for Serious Adverse Events

All SAEs, except those expected ones defined in section 10.1.5 that do not require immediate reporting (see 10.1.5), must be reported to the Sponsor within one working day of discovery or notification of the event. The Sponsor will perform an initial check of the information and ensure that it is reviewed at the next R&I Management meeting. All SAE information must be recorded on an SAE form and sent to the Sponsor using the appropriate reporting form and the contact details on there. Additional information received for a case (follow-up or corrections to the original case) needs to be detailed on a new SAE form which must be sent to the Sponsor using the appropriate reporting form and the contact details on there.

The Sponsor will report all SUSARs to the Research Ethics Committee concerned. Fatal or life-threatening SUSARs must be reported within 7 days and all other SUSARs within 15 days. The CI will inform all investigators concerned of relevant information about SUSARs that could adversely affect the safety of participants.

In addition to the expedited reporting above, the CI shall submit once a year throughout the study or on request an Annual Report to the Ethics Committee which lists all SAEs / SUSARs that have occurred during the preceeding 12 months.

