11.3 The Level of Statistical Significance

Alpha error of 5%, beta error 20%, power 80%

11.4 Criteria for the Termination of the Trial.

The trial will be terminated when 10 non-pregnant volunteers and 30 post natal volunteers have completed the study protocol.

11.5 Procedure for Accounting for Missing, Unused, and Spurious Data.

The trial will be terminated once we have 40 complete data sets. There will be no unused data sets. Spurious data will be excluded from analysis and will require additional recruitment.

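### Adverse events need not be attributed to a needle, and draws that fail, clot or are excluded are not counted per needle

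*Combined protocol and SAP*

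**What the plan says.** Sections 6.1 and 8.4 give every participant both needles and alternate which is used first. On the sites, section 6.1 says: "The punctures will be from separate veins for each of the two needles".

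Section 10.2 requires every adverse event, attributed to the study or not, to go on the CRF. It then lists the items: "The following information will be recorded: description, date of onset and end date, severity, assessment of relatedness to study, other suspect device and action taken". It also says that a medically qualified investigator judges the relationship of events to the study.

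Section 10.1.5, which is headed as dealing with serious events, says: "The main issues to note would be difficult phlebotomy which would be uncomfortable and phlebotomy can lead to bruising. None of these would require reporting". Section 10.3 refers back to it: "All SAEs, except those expected ones defined in section 10.1.5 that do not require immediate reporting (see 10.1.5), must be reported to the Sponsor".

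On incomplete data, section 11.5 says: "The trial will be terminated once we have 40 complete data sets. There will be no unused data sets". It adds that spurious data are excluded and made up by further recruitment, but does not say what makes data spurious. Section 8.7 replaces withdrawn participants and destroys their data, while keeping the reason for withdrawal in the CRF.

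Section 4 explains why the new needle is being studied. The valve might activate clotting, and: "If this occurred it could reduce the time the clinician has to utilise the blood before it clots in the syringe".

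**The concern.** There are two gaps, and they compound each other.

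The first is attribution. Each participant is her or his own control, which is the ideal setting for comparing puncture-site problems between needles. Yet the causality judgement is made against the study as a whole. Both punctures are study procedures, so a bruise can be study-related whichever needle caused it, and that judgement cannot separate the two.

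The second is the denominator. The trial stops on a count of complete pairs, not of people punctured. A participant whose new-needle sample clotted, could not be drawn or was set aside as spurious is replaced by another. If such losses occurred mainly with the new needle and because of clotting, the report could show 40 clean pairs and omit the cases closest to the hazard in section 4. If the lost samples would also have had short R times, their removal would move the paired comparison towards no difference. The documents contain no data on whether this would happen.

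**Working it through.** The plan states no figure on this point, so the check is mainly a reading of the sections together.

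**Attribution**

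| Question | Where | Answer |
|---|---|---|
| Who is exposed to each needle? | 6.1, 8.4 | Everyone, to both |
| Are the sites distinct? | 6.1 | Yes, separate veins |
| Must adverse events be recorded? | 10.2 | Yes, all of them, on the CRF |
| Causality judged against what? | 10.2 | The study |
| Is needle, vein or order a required item? | 10.2 | No |
| Where could it still appear? | 10.2 | Free-text description, or the item on another suspect device |

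The design makes attribution easy, but the plan leaves it to whoever fills in the free text.

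**Counting**

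1. A failed draw followed by a successful repeat gives a complete pair. No section requires the failure to be noted.
2. A set judged spurious is excluded and replaced (11.5). No reason or needle has to be recorded.
3. A participant withdrawn after a failed draw is replaced and the data are destroyed, but the reason is recorded (8.7). Failed draw is not among the listed reasons, although the list is open, and the needle need not be named.
4. Section 11.7 analyses evaluable data up to 10 non-pregnant and 30 post natal completers. No count of people attempted is requested.

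**Reporting wording**

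Section 10.1.5 taken alone could be read as permission to leave out bruising and difficult phlebotomy. Section 10.2 makes no such exception, and section 10.3 uses 10.1.5 only to limit immediate reporting of serious events. The three sections can be reconciled, but 10.1.5 does not say so itself.

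**Illustration of size**

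Assume that a participant fails to give a complete pair with probability p, that failures are independent, and that each loses the participant with no repeat attempt. None of this is in the documents. Then:

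- expected failures before 40 complete pairs = 40p/(1 − p)
- participants needed = 40/(1 − p), rounded up
- chance of at least one failure among the first 40 = 1 − (1 − p)^40

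| Assumed p | Expected failures | Participants needed | Chance of at least one in 40 |
|---|---|---|---|
| 2% | 40 × 0.02/0.98 = 0.8 | 41 | 55% |
| 5% | 40 × 0.05/0.95 = 2.1 | 43 | 87% |
| 10% | 40 × 0.10/0.90 = 4.4 | 45 | 99% |

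A log is informative even when it is empty. With 0 failures in 40 people punctured, the one-sided 95% upper limit for the failure rate is 1 − 0.05^(1/40) = 7.2%. With no count of those attempted, no such limit can be given.

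**The case against.** The strongest reply is that the protocol sets out to compare clotting profiles (5.1), has no secondary objectives (5.2), and promises no comparative safety or usability claim. R time is its chosen measure of the hazard, and the hazard in section 4 is clotting in the syringe after aspiration, not a blocked valve. A failed draw may simply mean a difficult vein. This stands in part. It is why the log should record the reason for each failure, and why a failed draw should not be read as a clotting event by default. It does not explain how a reader would learn that clotted samples had been replaced.

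Three stronger readings are tempting, and the documents do not support them.

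- *A reader might infer that bruising and difficult phlebotomy go unrecorded.* Section 10.2 requires all adverse events on the CRF, and the definition in 10.1.1 is broad enough to cover bruising. Section 10.3 treats the 10.1.5 exemption as one from immediate reporting of serious events.
- *A reader might infer that events cannot be assigned to a needle, so that all 80 punctures (40 pairs × 2) give unusable safety data.* Separate veins and a free-text description would allow assignment if the site were written down. Only punctures with an event produce event data at all. The CRF is not among the documents, so it may hold more than 10.2 lists.
- *A reader might infer that failed draws leave no trace.* Failures that lead to withdrawal leave a recorded reason under 8.7 and could be tallied from it.

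It might also be proposed to replace relatedness to the study with relatedness to each needle. That would do harm: 10.1.2 uses relatedness to the study to define an adverse reaction, and 10.2 uses it to trigger follow-up.

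**Conclusion.** The point holds as a gap in what the plan requires. It does not show that the information will be lost. Attribution of puncture-site events to a needle is not guaranteed. Failed, clotted, repeated and excluded draws have no required per-needle count and no denominator of people attempted. Section 10.1.5 needs to be reconciled in words with 10.2 and 10.3.

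The size is unknown. At assumed loss rates of 2% to 10%, about 1 to 4 participants would be replaced before 40 pairs are reached. These rates, and the assumption of no repeat attempts, are illustrations only. Even a few such losses, if confined to the new needle and due to clotting, would matter to a reader judging that needle. The sample size and the paired R-time test do not change. The change is worth making because it costs little and affects what the trial can say about the new needle.

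**What to change.** - **10.2:** keep the assessment of relatedness to the study, and add to each adverse event entry the needle (standard or new), the puncture site and whether it was the first or second puncture.
- **8.7 and 11.5:** for everyone punctured, keep a log by needle of attempts, failed draws, visible clot, and exclusions with the reason. Define spurious data. State that this log is kept when a participant is withdrawn. Report it descriptively, with all attempted participants as the denominator, beside the 40 analysed pairs.
- **10.1.5:** state that the waiver concerns expedited reporting and not recording on the CRF.

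The cost is a few CRF fields filled in at the time of phlebotomy and one descriptive table. It needs no extra participants, visits or staff. The small downside is that the report may show a failure rate above zero.

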10.3 Reporting Procedures for Serious Adverse Events

All SAEs, except those expected ones defined in section 10.1.5 that do not require immediate reporting (see 10.1.5), must be reported to the Sponsor within one working day of discovery or notification of the event. The Sponsor will perform an initial check of the information and ensure that it is reviewed at the next R&I Management meeting. All SAE information must be recorded on an SAE form and sent to the Sponsor using the appropriate reporting form and the contact details on there. Additional information received for a case (follow-up or corrections to the original case) needs to be detailed on a new SAE form which must be sent to the Sponsor using the appropriate reporting form and the contact details on there.

The Sponsor will report all SUSARs to the Research Ethics Committee concerned. Fatal or life-threatening SUSARs must be reported within 7 days and all other SUSARs within 15 days. The CI will inform all investigators concerned of relevant information about SUSARs that could adversely affect the safety of participants.

In addition to the expedited reporting above, the CI shall submit once a year throughout the study or on request an Annual Report to the Ethics Committee which lists all SAEs / SUSARs that have occurred during the preceeding 12 months.

11. STATISTICS

11.1 Description of Statistical Methods

The primary outcome for this study is change in time to initiate clot formation, as measured by the R time using thromboelastography. As subjects are to be exposed to both study limbs the data collected will be analysed using paired tests for statistical differences. The variation is different for non-pregnant and post natal subjects, therefore we have calculated sample size for each of the two study populations separately. As the sample size is small it is unlikely that the results will be normally distributed, therefore non-parametric test will be employed. As the sample sizes are small we do not anticipate needing any interim analysis. There is no plan to compare non-pregnant and post natal groups, only the within group differences.

11.2 The Number of Participants

We have used established reference ranges for TEG parameters in pregnant and non-pregnant populations to allow us to calculate an estimated standard deviation of the difference in R times for paired data to inform our power calculation. To see a 25% reduction in R time, with an alpha error of 5% and a beta error of 20% (power 80%) we require 10 non-pregnant subjects and 30 post natal participants.

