5. OBJECTIVES

5.1 Primary Objectives

We aim to determine if there is a difference in the clotting profile values from blood extracted with a normal 21G hypodermic needle vs the new 21G non-Luer one-way filter valve needle.

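### The 80% power rests on a paired SD whose derivation is not reported, and with only significance tests planned a null result has nothing else to support it

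*Combined protocol and SAP*

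**What the plan says.** The primary outcome is the change in TEG R time between two needles used in the same person. Section 11.2 takes its variability from published ranges ("We have used established reference ranges for TEG parameters in pregnant and non-pregnant populations to allow us to calculate an estimated standard deviation"), and the quantity sought is the SD of the paired difference ("calculate an estimated standard deviation of the difference in R times for paired data to inform our power calculation"). The target is stated as "To see a 25% reduction in R time". With 5% alpha and 80% power (repeated in section 11.3), this gives 10 non-pregnant and 30 post natal participants.

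Section 11.1 says each group was sized separately and that only within-group differences will be examined. It calls for paired tests and adds: "therefore non-parametric test will be employed". The test is not named, and no effect estimate or confidence interval is promised.

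The protocol does not give the reference ranges, mean R, between-person SD, SD of the difference, within-person correlation or test repeatability, sidedness, or the formula.

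**The concern.** A reference range comes from single values in many people, so it carries between-person spread. A paired analysis depends on how far two samples from one person differ. Getting from the first to the second needs the correlation between the paired samples, and the protocol is silent on it. The reader cannot tell whether the 80% is cautious, about right or optimistic.

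This matters most if the result is null. The objective in section 5.1 is open ("We aim to determine if there is a difference in the clotting profile values"), and the background asks whether the valve activates clotting. If the test is not significant, the natural question is whether a 25% reduction has been ruled out. As the plan stands, the only thing that bears on that question is the planned power, which cannot be checked. Each group is analysed alone, so neither can make up for the other.

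**Working it through.** **Inputs from the protocol.** Alpha 5%, power 80%, 25% reduction, n = 10 and n = 30 (sections 11.2 and 11.3); paired design (section 11.1).

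**Assumptions of this check.** Two-sided test (the objective is a difference; sidedness is not stated); paired t-test as the sizing method; 10 and 30 as exact minima for 80% power; equal SDs for the two needles.

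**Can 10 and 30 be reproduced?** No. A forward calculation needs mean R and the SD of the difference, and neither is given. The check has to run backwards.

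**Step 1: implied SD of the difference.** Solving the noncentral t power equation for 80% gives the standardised effect d, and SD_diff = 25% / d.
- n = 10: d = 0.996, so SD_diff = 25 / 0.996 = 25.1% of mean R.
- n = 30: d = 0.529, so SD_diff = 25 / 0.529, about 47.2% of mean R.

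Other conventions move these figures: the normal approximation gives 28% and 49%, and a one-sided t-test gives 29% and 54%.

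**Step 2: the role of the correlation.** SD_diff = SD x sqrt(2(1 - rho)), where SD is between-person and rho is the correlation between one person's two samples. At rho = 0, SD_diff = 1.414 x SD; at rho = 0.5, SD_diff = SD; at rho = 0.75, SD_diff = 0.707 x SD. A step from 0.5 to either 0 or 0.75 therefore changes SD_diff by a factor of sqrt(2).

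**Step 3: power if the true SD_diff differs from the planned one by sqrt(2).**

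| True SD_diff / planned | Power, n = 10 | Power, n = 30 |
|---|---|---|
| 0.707 | 97.6% | 97.7% |
| 1 | 80% | 80% |
| 1.414 | 51.1% | 50.9% |

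A simulated signed-rank test on normal differences gives about 97%, 78 to 79% and 49% in the same three rows, so the choice of test matters little here.

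**Step 4: dependence on what was assumed.**
- Planned at rho = 0: power is 80% at a true rho of 0, 97.6% and 97.7% at 0.5, and never below 80% for rho of 0 or more.
- Planned at rho = 0.5 (between-person SD used directly): about 63% at a true rho of 0.25 and 51% at 0, in both groups.
- Planned at rho = 0.8: about 43% at a true rho of 0.5 and 24% at 0.

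**Step 5: what a confidence interval would show.** Half-width = t(0.975, n - 1) x SD_diff / sqrt(n), in % of mean R.
- Planned SD, n = 10: 2.262 x 25.1 / 3.162 = 18.0%. n = 30: 2.045 x 47.2 / 5.477 = 17.6%.
- SD larger by sqrt(2), n = 10: 2.262 x 35.5 / 3.162 = 25.4%. n = 30: 2.045 x 66.8 / 5.477 = 24.9%.

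With the larger SD, an observed change of exactly zero fails to exclude a 25% reduction at n = 10 and barely excludes it at n = 30. With the planned SD it excludes it comfortably in both groups.

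**The case against.** The strongest reply is that this is unreported detail, not a demonstrated error. Section 11.2 says the ranges were used to allow a calculation, and a between-person SD plus an assumed correlation would give exactly the quantity named. The planners may have made that assumption without writing it down. If they took the samples as independent, the sizing is conservative. The back-solved figures lean mildly that way for the post natal group. A between-person SD of 47.2% implies a symmetric 95% range of about 7% to 193% of the mean (1.96 x 47.2 = 92.5), whereas planning at zero correlation implies an SD of 33.4% and a less strained range of about 35% to 165%. Round sample sizes may also have been rounded up, in which case power at the planning values exceeds 80%. All of this stands, and it rules out saying that the study is underpowered.

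A reader might take 51% and 98% as limits on the true power. They are not: they illustrate one size of error in each direction, and Step 4 shows values outside them under other guesses.

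A reader might also infer that antenatal ranges were applied to a post natal group, because section 11.2 refers to pregnant populations. The protocol uses that word for the post natal arm itself in sections 8.2 and 8.6, so the inference is not supported.

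Finally, no section says that a null result will be presented as reassurance. That is true, but nothing in the plan prevents it or supplies a better basis.

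**Conclusion.** The point holds in a limited form. The stated source cannot yield a paired SD without a within-person correlation, and none is reported, so the 80% power cannot be verified. It is not shown to be wrong. How much this matters depends on the unreported assumption: an SD of the difference misjudged by sqrt(2) moves power to about 51% or 98%, while planning at zero correlation would leave it at 80% or more for any non-negative correlation. These figures rest on a two-sided paired t-test and on 10 and 30 being exact minima.

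The practical consequence lies in the analysis. With only significance tests planned, a non-significant result would lean on that unverified power. In the unfavourable illustration the data could not clearly rule out the plan's own 25% reduction, even with no observed change. A confidence interval would show this directly from the data, whatever was assumed at planning.

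**What to change.** In section 11.1, commit to reporting for each group the observed SD of the paired differences and a 95% CI for the percentage change in R time, for example the Hodges-Lehmann interval that matches the signed-rank test if that is the test chosen. State that no important reduction will be concluded only if this interval excludes a 25% reduction, and not from a non-significant p-value or from the planned power.

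In section 11.2, give for each group the mean R, SD, within-person correlation and sidedness that were assumed, and describe the 80% as conditional on them. Keep the sample sizes at 10 and 30.

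The cost is a little more analysis and a rewritten paragraph, with no extra participants. The downside is that a null result may have to be reported as inconclusive.
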